#### 6.1.1 Televisit #1a:

After signing the eIC, the following will be administered/obtained/collected by a trained assessor at televisit, unless otherwise noted ([Table 1](#)):

- Demographic information and Height
- Medical/Psychiatric/Social History
- Reproductive/Menstrual Cycle History Questionnaire; biological females only
- MINI-AS
- Prior Medications (past 12 months) and Concomitant Medications
- C-SSRS 'Baseline/Screening' Version
- Review Inclusion and Exclusion Criteria

	Protocol 812P413	
	Page 25 of 61	Version 2.0

## 6.2 Treatment Period

The first shipment will contain sufficient medication for the first 4 weeks of the study, after which, two more shipments will be triggered for ongoing treatment based on participant response and PI or designee's prescription.

Once study medication is received, the participant will confirm receipt and administration of the first dose within the study mobile app. At all other timepoints, dosing information will be captured during the televisit.

A televisit will be scheduled 4 weeks (28 days), 9 weeks (63 days ) and 14 weeks (98 days) after date of first dose ([Table 1](#), [Figure 1](#)). Participants will need to continue to take study medication as per the instructions provided by the Investigator during the Treatment Period.

	Protocol 812P413	
	Page 26 of 61	Version 2.0

During the Televisit #2 and #3 (Weeks 4 and 9), the following will be administered, obtained or collected by a qualified/trained rater or assessor (ClinRO efficacy assessments should not be administered if participant is discontinuing and has not taken daily dose of Qelbree for >7 consecutive days prior to the televisit):

- AISRS
- CGI-S
- CGI-C
- C-SSRS '*Since Last Visit*' Version
- Review AEs
- Review Concomitant Medications
- Report systolic/diastolic blood pressure, pulse rate, and weight
- Report UPT results (FOCPs only)
- RMCH Questionnaire's Menstrual-Question #5 (FOCPs only)
- SM accountability; Report the number of remaining capsules in bottle
- Confirm or reschedule next virtual visit (Week 9 and Week 14, as applicable)

In addition, at Weeks 4 and 9, the participant will complete the following via the study mobile app (PRO efficacy assessments should not be administered if participant is discontinuing and has not taken daily dose of Qelbree for >7 consecutive days prior to attempting them):

- SM administration mode/time query; report admin method and average admin time
- ASRSv1.1-SC
- PHQ-8
- GAD-7
- WPAI:SHP

During the treatment period, participants should continue all current medications or other treatment regimens as prescribed by their primary care physician. Their primary care physician will determine changes to these regimens according to routine clinical practice, but participants should be reminded to report changes in concomitant medications (e.g., new medication started, current medication discontinued, or dose reduced, etc.) to the study staff between televisits. Participants may withdraw consent or PI/designee can discontinue a participant if they feel it is no longer in the best interest of the participant to continue in the study. If the participant's participation ends prior to Week 14 of treatment, the reason for discontinuation will be captured by the study staff.

### 6.3 End of Study

During the Televisit #4 (Week 14/EOS), the following will be administered, obtained or collected by a qualified/trained rater ([Table 1](#); ClinRO efficacy assessments should not be administered if participant has not taken daily dose of Qelbree for >7 consecutive days prior):

- AISRS
- CGI-S
- CGI-C
- SIGMA

	Protocol 812P413	
	Page 27 of 61	Version 2.0

- SIGH-A
- C-SSRS '*Since Last Visit*' Version
- Review AEs
- Review Concomitant Medications
- Report systolic/diastolic blood pressure, pulse rate, and weight
- Report UPT results (FOCPs only)
- RMCH Questionnaire's Menstrual-Question #5 (FOCPs only)
- SM accountability; report the number of remaining capsules in bottle
- Schedule safety follow-up televisit

In addition, at Week 14/EOS, the participant will complete or report the following via the study mobile app (efficacy assessments should not be administered if participant has not taken daily dose of Qelbree for >7 consecutive days prior):

- SM administration mode/time query; report admin method and average admin time
- ASRSv1.1-SC
- PHQ-8
- GAD-7
- WPAI:SHP
- PSQI
- BRIEF-A

If participant discontinues early (Early-Termination), perform Week 14 assessments; however, ClinRO/PRO efficacy assessments should not be administered if participant has not taken daily dose of Qelbree for >7 consecutive days prior.

#### **6.4 Safety Follow-up (SF) Televisit**

A week following participant's last dose of study medication, a safety follow-up televisit will be conducted to review AEs and Concomitant Medications ([Table 1](#)).

	Protocol 812P413	
	Page 28 of 61	Version 2.0

**Table 1. Schedule of Events**

Study Period	Screening Period			Treatment Period			EOS 	SF
Week of Study	–	–	–	–	4	9	14	15
Televisit  No.	1a	1b	–	–	2	3	4	5
Day of Study	- 28 to -1		- 7 to -1	1	29	64	99	106
Window (days)	–	–	–	–	± 3	± 3	± 3	± 3
Informed Consent	X							
Schedule Next Televisit	X	X			X	X	X	
Review Inclusion/Exclusion Criteria	X	X						
Demographics	X							
Medical/Psychiatric/Social History	X							
RMCH Questionnaire	X 	X 			X 	X 	X 	
Review Prior Medications 	X							
Review Concomitant Medications	X	X			X	X	X	X
Review Adverse Events					X	X	X	X
Ship BP/PR cuff 	X							
Ship UPT (FOCP only) 	X							
Confirm Negative UPT (FOCP only)	X				X	X	X	
BP/PR and Weight 	X				X	X	X	
Height 	X							
MINI-AS (DSM-5-TR)	X							
AISRS ( ClinRO )		X			X	X	X	
CGI-S ( ClinRO )		X			X	X	X	
CGI-C ( ClinRO )					X	X	X	
SIGMA ( ClinRO )		X					X	
SIGH-A ( ClinRO )		X					X	
C-SSRS (Baseline/Screening version)	X							
C-SSRS (Since Last Visit version)		X			X	X	X	
Mobile App Training Module (PROs)		X						
Dispense SM			X		X	X		
First Dose of Qelbree 				X				
ASRSv1.1-SC (PRO) 		X			X	X	X	
PHQ-8 (PRO) 		X			X	X	X	

	Protocol 812P413	
	Page 29 of 61	Version 2.0

Study Period	Screening Period			Treatment Period			EOS 	SF
Week of Study	–	–	–	–	4	9	14	15
Televisit  No.	1a	1b	–	–	2	3	4	5
Day of Study	- 28 to -1		- 7 to -1	1	29	64	99	106
Window (days)	–	–	–	–	± 3	± 3	± 3	± 3
GAD-7 (PRO) 		X			X	X	X	
WPAI:SHP (PRO) 		X			X	X	X	
PSQI (PRO) 		X					X	
BRIEF-A (PRO) 		X					X	
SM Administration Mode/Time 					X	X	X	
SM Accountability					X	X	X	
Participant Ship/Return Unused SM 							X	

**Abbreviations:** AISRS = Adult ADHD Investigator Symptom Rating Scale; ASRSv1.1-SC = Adult ADHD Self-Report Scale Version 1.1 Symptom Checklist; BRIEF-A = Behavior Rating Inventory of Executive Function-Adult Version; BP = Blood Pressure (systolic/diastolic); CGI-S = Clinical Global Impression Scale of Severity; CGI-C = Clinical Global Impression Scale of Change; C-SSRS = Columbia Suicide Severity Rating Scale; ClinRO = Clinician-Reported Outcomes; EOS = end of study; FOCP = Females of Childbearing Potential; GAD-7 = General Anxiety Disorder-7 item; MINI-AS = Mini International Neuropsychiatric Interview for ADHD Studies; PHQ-8 = Patient Health Questionnaire 8-item; PRO = Patient-Reported Outcomes; PSQI = Pittsburgh Sleep Quality Index; PR = Pulse Rate; RMCH = Reproductive/Menstrual Cycle History; RMCH mQ5 = RMCH Questionnaire (Menstrual-Question #5); SF = Safety follow-up; SIGH-A = Structured Interview Guide for the Hamilton Anxiety Scale; SIGMA = Structured Interview Guide for the Montgomery and Åsberg Depression Rating Scale; SM = study medication; UPT = Urine Pregnancy Test; WPAI:SHP = Work Productivity and Activity Impairment: Specific Health Problem Questionnaire.

**Footnotes:**

1. Virtual televisits will last between 45 to 120 minutes. Consent will occur on or before Telehealth Visit 1a.
2. Administer full/entire RMCH Questionnaire (1 up to 8 items) to biological females at Screening only (if not administered at Televisit #1a, administer at Televisit #1b).
3. Only administer the RMCH mQ5 to FOCPs at Televisit #2, #3, and #4 during Treatment [Week 4, Week 9, and Week 14/EOS, respectively].
4. All medications (especially stimulant or non-stimulant ADHD medications) taken 12 months prior to Screening.
5. BP/PR cuff (and UPT) will be shipped once participant is determined eligible. Prior to taking first dose, participant will measure and record BP/PR and weight (and confirm a negative UPT).
6. Weight will be collected with shoes off. BP/PR will be measured in a seated position. Self-reported by the participant to the study team on Day 1 and thereafter reported during scheduled televisits.
7. Height (with shoes off) will be self-reported to the study team.
8. Participant will need to report time, date, and dose of SM within the study mobile app on Day 1
9. PROs and questions about SM administration method and timing will be completed in the study mobile app.
10. At Week 14 the participant will be required to return all SM to Sponsor for destruction upon confirmation of proper SM accountability.
11. If participant discontinues early (Early-Termination), perform Week 14 assessments; however, ClinRO/PRO efficacy assessments should not be administered if participant has not taken daily dose of Qelbree for >7 consecutive days prior.

	Protocol 812P413	
	Page 30 of 61	Version 2.0

## 7. Study Population

### 7.1 Inclusion Criteria

To be eligible for participation in this study, a participant must meet all of the following criteria:

1. Is male or female,  $\geq 18$  years of age.
2. Is willing and capable to provide and sign electronic informed consent.
3. Has a primary diagnosis of ADHD based on the Diagnostic and Statistical Manual of Mental Disorders; Fifth Edition, Text Revised (DSM-5-TR) as confirmed with the Mini-International Neuropsychiatric Interview for ADHD Studies (MINI-AS).
4. Has an AISRS Total score  $\geq 24$  at Screening.
5. Has a CGI-S score  $\geq 3$  at Screening.
6. Has a MADRS (SIGMA) Total score  $> 22$  at Screening and/or HAM-A (SIGH-A) Total score  $> 22$  at Screening.
7. If potential participant is a biological female, one of the following (a, b, or c) must be met:
  - a. Has undergone menopause, defined as a biological female who reports amenorrhea for at least 12 consecutive months prior to providing informed consent.
  - b. Is a non-pregnant Female of Childbearing Potential (FOCP) who is not seeking fertility treatment during the study and agrees to use one of the following acceptable birth control methods beginning 14 days prior to the first dose of study medication, throughout the study while taking study medication, and for 7 days following the last dose of study medication:
    - i. Hormonal contraceptive
    - ii. Barrier method: simultaneous use of male condom and diaphragm or cervical cap with spermicidal foam/gel/film/cream/suppository.
  - c. Has had bilateral tubal ligation, hysterectomy, bilateral oophorectomy (permanently sterilized) at least 6 months prior to providing informed.
8. If potential participant is a biological male, one of the following must be met:
  - a. Is capable of having children and agrees to use 2 methods of contraception beginning 14 days prior to the first dose of study medication, throughout the study while taking study medication, and for 7 days following the last dose of study medication.
  - b. Has had sterilization surgery (permanently sterilized) at least 6 months prior to providing informed consent.
9. Owns a functioning smartphone device, has access to an internet connection (Wi-Fi or data plan), is willing to download and use the study mobile app throughout the study,

	Protocol 812P413	
	Page 31 of 61	Version 2.0

and is willing to have visual telemedicine appointments (televisits) at times designated in the study protocol.

## 7.2 Exclusion Criteria

A participant who meets any of the following criteria will be excluded from participation in the study:

1. Has a history of substance use disorder (alcohol, opioids, etc.) within the last 6 months prior to providing informed consent with exception of nicotine and cannabis.
2. Is currently taking or has taken Qelbree for treatment of ADHD in the last 3 months or is currently taking another non-stimulant medication for treatment of ADHD, like atomoxetine (Strattera), Clonidine (Catapres, Kapvay) or Guanfacine (Tenex, Intuniv). Stimulant medications for ADHD and most medications for mood symptoms (symptoms of depression and/or anxiety) are allowed.
3. Is taking a prohibited concomitant medication per the Qelbree Prescribing Information.
4. Is a FOCP who is pregnant, nursing, sexually active with a male partner and not willing to use one of the acceptable birth control methods throughout the study and/or is seeking fertility treatment.
5. Has history of moderate or severe head trauma or other neurological disorder or systemic medical disease that, in the Investigator's opinion, is likely to affect central nervous system functioning. This would include participants with:
  - a) A current diagnosis of a major neurological disorder; or
  - b) Seizures, seizure disorder or seizure-like events; or a history of seizure disorder within the immediate family (siblings, parents); or
  - c) Encephalopathy
6. Has attempted suicide within the 6 months prior to the C-SSRS assessment at Screening, or is at significant risk of suicide, either in the opinion of the Investigator or defined as a "yes" to suicidal ideation questions 4 or 5 or answering "yes" to suicidal behavior on the C-SSRS within the 6 months prior to the C-SSRS assessment at Screening.
7. Is currently participating in another clinical trial or has participated in a clinical trial within the 60 days prior to providing informed consent.
8. Has any history of schizophrenia, schizoaffective disorder, or bipolar disorder, or has any other psychiatric disorders in the Investigator's clinical judgement would interfere with their ability to participate in the study.
9. Has any unstable, clinically significant cardiovascular condition that in the Investigator's clinical judgement would preclude their participating in the study.
10. Has any disease or taking any medication that could, in the Investigator's opinion, interfere with the assessments of safety, tolerability, or efficacy, or interfere with study conduct or interpretation of results.
11. History of unexplained loss of consciousness, unexplained syncope, unexplained irregular heartbeat or palpitations or near drowning with hospital admission.

	Protocol 812P413	
	Page 32 of 61	Version 2.0

12. In the Investigator's opinion, is unlikely to comply with the protocol or is unsuitable for any other reason.

### 7.3 Screen Failures

Participants who are consented to participate in the clinical trial, who do not meet one or more criteria required for participation in the trial during the screening procedures, are considered screen failures.

On a case-by-case basis, participants who previously screened for this study (e.g., provided informed consent), but were not dispensed SM may be allowed to rescreen for this study, but only after receiving written permission from sponsor and medical monitor.

### 7.4 Recruitment and Retention

Participants will be targeted for recruitment using digital and social media advertisements, and referrals from physicians' existing patient pool, within the contiguous US. A sufficient number of individuals will be screened to obtain up to 750 participants who will be dosed. An anticipated attrition rate of 33% is expected to result in the completion of up to 500 participants through the treatment period (14 weeks). Participants will have completed the study upon completion of all study procedures, assessments, and observations through the end of Week 14 of treatment.

## 8. Study Treatment

### 8.1 Study Treatment Description

Qelbree (viloxazine extended-release capsules) is a selective norepinephrine reuptake inhibitor indicated for the treatment of ADHD in adults and pediatric patients 6 years and older. Qelbree received marketing approval in the US in 2021 for pediatric patients 6-17 years of age, and in 2022 for adults  $\geq 18$  years of age ([Qelbree PI](#)).

### 8.2 Study Treatment Administration

#### 8.2.1 Study Medication

Qelbree (viloxazine extended-release capsules) is supplied in 100 mg, 150 mg, and 200 mg capsules ([Qelbree PI](#)).

#### 8.2.2 Dosing

Participants will be instructed to take Qelbree 200 mg once daily (QD) in the morning during Week 1 and 400 mg QD in the morning during Week 2 onwards until next contact with Investigator. The investigator may adjust/titrate dosage in increments of up to 200 mg weekly to the maximum recommended dosage of 600 mg once daily, depending on response and tolerability. At the discretion of the Investigator based on tolerability, the participant may be

	Protocol 812P413	
	Page 33 of 61	Version 2.0

instructed to take total daily dose once daily in the evening. See full prescribing information for Qelbree regarding participants who have severe renal impairment.

### 8.2.3 Mode of Administration

Qelbree is administered orally, with or without food. Qelbree capsules should not be cut, crushed, or chewed. Qelbree capsules should be swallowed whole, and if swallowing the capsule(s) whole is difficult, the capsule(s) can be opened, and the entire contents can be sprinkled over a teaspoonful or tablespoonful of pudding or applesauce. This mixture must be consumed entirely, without chewing, within 15 minutes for pudding or within 2 hours for applesauce. This mixture must not be stored for future use.

At Week 4, 9 and 14, participant will report the method of oral administration that was used during the past 4-5 weeks of treatment, e.g., in the past 4 or 5 weeks: (a) I swallowed intact capsule whole each time; (b) I swallowed food mixture each time; or (c) I used both methods to swallow study medication. In addition, at Week 4, 9 and 14, the participant will report the average clock time (hh:mm AM/PM) or time of day range that he/she took their daily dose of study medication during past 4-5 weeks.

For warnings and precautions, refer to full prescribing information for Qelbree.

## 8.3 Study Product Preparation/Handling/Storage/Accountability

Qelbree (viloxazine extended-release capsules) are available in the following strengths and colors:

- 100mg (yellow capsule printed with "SPN" on capsule cap and "100" on capsule body with edible black ink).
- 150mg (lavender capsule printed with "SPN" on capsule cap and "150" on capsule body with edible black ink).
- 200mg (light green capsule printed with "SPN" on capsule cap and "200" on capsule body with edible black ink).

### Storage and Handling

- Qelbree should be stored at 20°C to 25°C (68°F to 77°F); excursions are permitted between 15°C to 30°C (59°F to 86°F).

## 8.4 Concomitant Diets, Treatments, and Medications

### 8.4.1 Contraindications

Qelbree is contraindicated in participants:

- receiving concomitant treatment with monoamine oxidase inhibitors (MAOI), or within 14 days following discontinuing an MAOI, because of an increased risk of hypertensive crisis.

	Protocol 812P413	
	Page 34 of 61	Version 2.0

- receiving concomitant administration of sensitive CYP1A2 substrates or CYP1A2 substrates with a narrow therapeutic range.

For drug interactions, refer to [full prescribing information for Qelbree](#).

Furthermore, participants that are currently undergoing treatment for substance use disorder (if participant is stable/in recovery; with or without medication-assisted treatment), may be allowed to participate in this study on a case-by-case basis with Sponsor input.

All concomitant medications will be recorded in the eCRF. If a participant is taking a stimulant medication that is commercially available in a **short-acting** (immediate-release) and a **long-acting** (extended-release, prolonged release, etc.) formulation, also record in parentheses next to the name of stimulant in ConMeds page in participant's eCRF whether the participant's stimulant medication is either a short-acting [e.g., methylphenidate (IR), amphetamine [IR], etc.] or a long-acting [i.e., methylphenidate (ER), amphetamine [XR], etc.) formulation.

## 9. Study Assessments and Procedures

### 9.1 Screening Assessments

#### 9.1.1 Psychiatric Diagnostic Instruments

##### 9.1.1.1 Mini-International Neuropsychiatric Interview for ADHD Studies (MINI-AS)

The Mini International Neuropsychiatric Interview (MINI) was developed and designed as a brief structured diagnostic interview for the major psychiatric disorders in DSM-III-R, DSM-IV and DSM-5 and ICD-10 ([Sheehan et al., 1997](#); [Lecrubier et al., 1997](#); [Sheehan et al., 1998](#)). Validation and reliability studies have shown that the MINI has similar reliability and validity properties to similar instruments, however administration duration of time of the MINI is much shorter than the other diagnostic instruments. The standard MINI assesses the 17 most common mental health disorders (e.g., current prevalence rates of 0.5% or higher in the general population in epidemiology studies) using branching tree logic. Compared to the standard MINI, the MINI-AS version has a more detailed set of questions for each of the nine Psychotic Disorders. It is suitable for clinical and research settings where Psychotic Disorders are a focus of interest and where it is important to differentiate between the different psychotic disorders (e.g., schizophrenia vs schizoaffective disorder). The standard MINI does assess both Major Depressive Disorder with Psychotic Features and Bipolar I Disorder with Psychotic Features. Otherwise, all the other modules are similar to the standard MINI.

As outlined in [Section 6.1.1](#), a diagnosis of ADHD is confirmed via MINI-AS by trained central assessor/psychiatrist.

	Protocol 812P413	
	Page 35 of 61	Version 2.0

## 9.2 Efficacy Assessments

### 9.2.1 Clinician-Rated Outcomes (ClinROs)

As outlined in [Section 6.1.2](#), once a diagnosis of ADHD is confirmed, all clinician-rated outcome assessments will be administered by trained central raters or psychiatric nurse practitioners for reliability of data captured. ClinRO efficacy assessments should not be administered if participant is discontinuing and has not taken daily dose of Qelbree for >7 consecutive days prior to televisit.

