## **10. Study Completion and Discontinuation**

### **10.1 Study Completion**

Participants that take study medication until Week 14/EOS and complete most study procedures (e.g. safety and ClinROs) by the end of the 14-week treatment period will be

	Protocol 812P413	
	Page 46 of 61	Version 2.0

considered to have completed the study. Participants that choose to discontinue study medication prior to Week 14, will be withdrawn from the study and reasons for discontinuation will be noted in the eCRF.

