## 10.2 Study Discontinuation

The participant may withdraw themselves from the study at any time by notifying the study team. Participants may be discontinued from the study by the Investigator or designee if study procedures have not been followed or if the Investigator or designee determines the participant is not able to safely continue with the study due to an AE or other health-related issue.

Reasons for participant's study discontinuation may include:

- Withdrawal of consent (the reason for withdrawal of consent should be captured)
- Adverse event(s)
- Lack of efficacy
- Noncompliance with study procedures
- Lost to follow-up (the Investigator will document efforts to attempt to reach the participant by phone, email, and chat via study mobile app prior to considering that participant lost to follow-up)
- Other

After a participant has been discontinued, they will not be allowed to re-screen for enrollment in the study, unless there is a technical issue. The reasons for discontinuation will be documented in the participant's study record. Participants enrolled in error may be discontinued from the study with agreement from the Investigator and Sponsor.

If a participant is discontinued for any reason other than lost to follow-up, Week 14 procedures should be completed, and any outstanding data recorded in their record. If a participant is withdrawn at any stage during the study due to an AE, the Investigator or designee will advise the participant of appropriate follow-up with a local doctor, if needed. If a participant's involvement in the study ends prior to resolution of an event, the event will be marked as ongoing and the Investigator or designee will advise the participant of appropriate follow-up (e.g., to provide follow-up information/referral to the participant's primary care physician). The status of the AE at the last follow-up will be documented. The reason for discontinuation and efforts to follow participants who discontinue because of AEs will be fully documented.

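### Efficacy scales are withheld at attended visits once a participant is more than 7 days off drug, and the Week 14 condition differs from the one used elsewhere

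*Protocol*

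**What the plan says.** The protocol states the bar in several places.

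- **9.2.1 (clinician-rated scales):** "ClinRO efficacy assessments should not be administered if participant is discontinuing and has not taken daily dose of Qelbree for >7 consecutive days prior".
- **6.2 (Weeks 4 and 9):** clinician ratings are withheld if the "participant is discontinuing and has not taken daily dose of Qelbree for >7 consecutive days prior to the televisit". The app-based scales follow the same pattern: "PRO efficacy assessments should not be administered if participant is discontinuing and has not taken daily dose of Qelbree" for more than 7 days. Section 9.2.2 repeats this for the treatment period.
- **6.3 (Week 14/EOS):** "ClinRO efficacy assessments should not be administered if participant has not taken daily dose of Qelbree for >7 consecutive days prior". The discontinuing condition is absent, and the app-based scales at that visit are treated the same way.
- **6.3 and Table 1 footnote 11 (early termination):** "If participant discontinues early (Early-Termination), perform Week 14 assessments; however, ClinRO/PRO efficacy assessments should not be administered" after more than 7 days without drug.
- **10.2:** "If a participant is discontinued for any reason other than lost to follow-up, Week 14 procedures should be completed", with no 7-day exception in that section.
- **10.1:** "Participants that choose to discontinue study medication prior to Week 14, will be withdrawn from the study".

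In the SAP, the Full Analysis Set needs a baseline and at least one post-baseline AISRS (5.3). Missing-data rules for efficacy work within a scale and do not cover a missing visit (5.6.1). Early-termination visits go to the next scheduled visit (5.7). The Week 14/EOS AISRS change gets a nominal one-sample t-test and 95% CI (7.1).

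**The concern.** The bar applies to someone who is present at a televisit, and it is triggered by having stopped drug. Not taking the rating is a choice made by the plan, and the value cannot be recovered afterwards. A rating that is taken and flagged can still be left out of an on-drug summary.

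Three things are at stake. First, the study has one arm and reports observed means, so if barred participants did worse than those rated, nothing in the analysis would show it or correct for it. Second, anyone barred before a first post-baseline AISRS drops out of the analysis set used for every efficacy endpoint. Third, MADRS, HAM-A, PSQI and BRIEF-A are scheduled after baseline only at Week 14/EOS or early termination, so a barred leaver has no post-baseline value on them at all. MADRS and HAM-A are the scales that define the mood-symptom population (inclusion criterion 6).

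Separately, the two forms of the condition give raters conflicting instructions for the same participant at Week 14.

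**Working it through.** **Wording, side by side**

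| Place | Must be discontinuing? | More than 7 days off drug? |
|---|---|---|
| 6.2, Weeks 4 and 9 | yes | yes |
| 9.2.1, clinician-rated scales | yes | yes |
| 9.2.2, patient-reported scales | yes | yes |
| 6.3, Week 14/EOS | no | yes |
| 6.3 and footnote 11, early termination | leaving by definition | yes |

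Take a participant who has a gap of more than 7 days before a visit and intends to continue. At Weeks 4 and 9 this person is rated. At Week 14 the person is barred under 6.3 but not under 9.2.1 or 9.2.2. The texts cannot all be followed.

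**The plan's own figure**

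750 × (1 − 0.33) = 502.5, against the stated 500 completers. In reverse, 500 / (1 − 0.33) = 746.3, so 747, against the stated 750. The figures agree. I use 502 completers and 750 − 502 = 248 leavers.

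**Who can reach the Week 14 AISRS mean**

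Under SAP 5.7, an early-termination rating before Week 4 is summarised at Week 4, and one between Weeks 4 and 9 at Week 9. Only leavers after Week 9 map to Week 14. The documents do not say when people leave. Assuming an even spread over 14 weeks, 248 × 5/14 = 88.6, about 89.

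**Illustrative inputs**

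- Completers' mean change: −15.5 (active arm of Study 812P306, Protocol 3.2.2).
- Barred leavers' mean change c: −11.7 (placebo arm of that study) or −5 (assumed).
- Share of the 89 who attend but are barred: 25% to 75% (assumed), so b = 22 to 66.

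**Formula and results**

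Shift = pooled mean of completers and barred leavers, minus the completer mean = b × (c + 15.5) / (502 + b).

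- c = −11.7, b = 22: 22 × 3.8 / 524 = 0.16
- c = −11.7, b = 66: 66 × 3.8 / 568 = 0.44
- c = −5, b = 22: 22 × 10.5 / 524 = 0.44
- c = −5, b = 66: 66 × 10.5 / 568 = 1.22
- c = −15.5: 0 for any b. If barred leavers improved more than completers, the sign reverses.

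This leaves the other late leavers out of both means. If they are instead rated and counted with the same c, the shift is 89(c + 15.5)/591 − (89 − b)(c + 15.5)/(591 − b):

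- c = −11.7: 0.57 − 0.45 = 0.12 (b = 22) and 0.57 − 0.17 = 0.41 from unrounded values (b = 66)
- c = −5: 1.58 − 1.24 = 0.34 (b = 22) and 1.58 − 0.46 = 1.12 (b = 66)

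The order of size is the same.

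I give no figure for the scales scheduled only at Week 14/EOS. The documents offer no mean changes for them, and SAP 5.7 does not say how an early-termination rating on them before Week 9 would be shown.

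**The case against.** The best defence is that the bar is an on-treatment choice. The SAP has AISRS and ASRSv1.1-SC rated over the past week, so after more than 7 days off drug the recall window holds no treated day. The study is open-label and descriptive, with no formal hypotheses and no power basis. This defence is fair for those two scales. It fits GAD-7 (2 weeks), BRIEF-A and PSQI (a month) less well, because at 8 days off drug part of the recall period is still on drug. Neither document states an on-treatment target or gives a reason for the bar.

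Four stronger readings are tempting, and the documents do not support them.

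- **That all leavers distort the Week 14 mean.** Placing 25-75% of all 248 leavers (62 to 186) there would give 0.4-1.0 points at −11.7 and 1.2-2.8 at −5. SAP 5.7 rules this out. Much Week 14 loss would also remain without the bar, because people who stop drug are withdrawn.
- **That the rule removes non-responders and intolerant participants, and so must favour the drug.** The test is days since last dose, not the reason for stopping. Someone who stops for lack of efficacy or an adverse event and is seen within 7 days is still rated. Earlier Week 4 or Week 9 ratings stay in the summaries. A favourable shift is plausible but not derivable.
- **That 10.2 is a third, conflicting version.** It can be read as pointing to the Week 14 procedures in 6.3, which carry the exception.
- **That the shift can be judged against the 3.7-point difference in 812P306.** That is a between-arm difference, from a trial that excluded depression and anxiety. A shift in a single-arm mean is a different quantity.

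The 25-75% share has no source in the documents. Leavers lost to follow-up have no visit to be barred from.

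**Conclusion.** The point holds on two counts. The condition for withholding efficacy scales is inconsistent between 6.3 at Week 14 and 6.2, 9.2.1 and 9.2.2. Also, outcomes of people who stopped drug go uncollected at visits they attend, with no visit-level remedy in the SAP.

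The effect on the Week 14 AISRS mean cannot be derived. It is about 0.2-0.4 points (barred leavers at −11.7) or 0.4-1.2 points (at −5), given evenly spread leaving, 25-75% of late leavers barred and completers at −15.5. It is zero if barred leavers improved as much as completers. The loss is most complete for MADRS, HAM-A, PSQI and BRIEF-A, where a barred leaver contributes nothing after baseline, and for anyone barred before a first post-baseline AISRS, who leaves the analysis set.

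**What to change.** **Protocol.** Reconcile 6.2, 6.3, 9.2.1, 9.2.2 and Table 1 footnote 11 into one assessment rule: administer the scheduled efficacy scales at every attended Week 4, 9, 14 or early-termination visit, and record days since last dose. A cross-reference from 10.2 to that rule would remove any doubt there. The change concerns assessment only and leaves dosing and discontinuation rules untouched.

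**SAP 7.1 and 7.2.** Present two summaries side by side: all collected ratings, and ratings with the last dose within 7 days. State which one the Week 14 t-test uses. That is a choice of what the study estimates, and the sponsor should make it explicitly.

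**Cost.** Amendment wording, one dataset flag and a second set of summary columns. Some early leavers will have longer televisits, and some ratings will be off drug, which the flag separates. The fix does not change SAP 5.7, so AISRS ratings from leavers before Week 9 will still appear at Week 4 or Week 9.
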